7.2.6 Other Concomitant Medications

Physicians will confirm subjects who take any non-opioid concomitant medication for pain at baseline, or who start it during the study, and will be asked to report the medication type. The following medication categories have been identified as common medication classes taken by chronic pain patients: Nonsteroidal Anti-inflammatory Drugs (NSAIDs) and Acetaminophen, Antidepressants, Anticonvulsants, Benzodiazepines and Muscle Relaxants. Physicians will be asked to report the medication type and total daily dose, and any changes throughout the study.

7.2.7 AEs/SAEs

All enrolled subjects and site physicians will receive guidance on AE reporting during the investigator training. Spontaneous AE reporting will be entered in *REDCap Cloud* by the subject, during at-home follow-up (subject to verification by physician at physician-verified follow-up). Physicians will classify each AE by seriousness, severity and inferred relation to the study product in the Physician AE form as described below. The GPVD will also review all SAEs with respect to applicable regulatory requirements.

7.2.7.1 AE Definition

An AE is any untoward medical occurrence in a subject administered a pharmaceutical product and which does not necessarily have a causal relation with treatment. An AE can therefore be any unfavorable and unintended sign, symptom, psychological effect, or disease associated with the use of a medicinal product, whether or not related to the medicinal product.

7.2.7.2 SAE Definition

An AE will be considered serious if it results in 1 or more of the following outcomes:

- Death
- Life-threatening (i.e., at immediate risk of death)
- Subject in-subject hospitalization or prolongation of existing hospitalization
- Persistent or significant disability/incapacity
- Congenital anomaly/birth defect
- Any other AE that the Investigator or company judges to be serious or which is defined as serious by the local regulatory agency.

Important AEs that may not result in death, be life threatening, or that do not require hospitalization may be considered serious when, based upon appropriate medical judgment, they may jeopardize the subject or may necessitate medical or surgical intervention to prevent one of the outcomes listed in the definition above. For this registry, the Important Medical Event (IME) list will be used as a reference for the assessment of medically significant adverse events³⁰.

7.2.7.3 AE Severity

The physician will assess the severity of all AEs reported in eCRFs as mild, moderate, or severe. For consistency, these intensity grades have been defined as follows:

- Mild:** An event that is usually transient and may require only minimal treatment or therapeutic intervention. The event does not generally interfere with usual activities of daily living.
- Moderate:** An event that is alleviated with additional specific therapeutic intervention. The event interferes with usual activities of daily living and may cause discomfort but poses no significant or permanent risk of harm to the subject.
- Severe:** An event that requires intensive therapeutic intervention. The event interrupts usual activities of daily living or significantly affects clinical status.

7.2.7.4 Relationship of AEs to Study Products

The physician will assess the relation of each AE/SAE to the study product after careful consideration and in accordance with the following guidelines:

Definitely related: The AE/SAE is clearly related to the study product (an alternative cause is unlikely).

Probably related: The connection to the study product can be made with a high degree of certainty. This causal relation is assigned when the AE/SAE meets the following criteria:

- Follows a reasonable temporal sequence from administration of the study product.
- Cannot be reasonably explained by the known characteristics of the subject's clinical state, environmental or toxic factors, or other modes of therapy administered to the subject.
- Follows a known pattern of response to the study product.
- Reappears upon subsequent challenge with the study product.

Possibly related: The connection to the study product appears unlikely but cannot be ruled out with certainty. This causal relation is assigned when the AE/SAE meets the following criteria:

- Follows a reasonable temporal sequence from administration of the study product.
- May have been produced by the subject's clinical state, environmental or toxic factors, or other modes of therapy administered to the subject.
- Follows a pattern of response to the study product.

Unlikely related: The AE/SAE is unlikely related to the study product when the AE or SAE meets the following criteria:

- Does not follow a reasonable temporal sequence from administration of the study product.
- May readily have been produced by the subject's clinical state, environmental or toxic factors, or other modes of therapy administered to the subject.
- Does not follow a known pattern of response to the study product.
- Does not reappear or worsen when the study product is re-administered.

Not related: The AE/SAE is judged to be clearly and incontrovertibly due only to a cause other than the study product (e.g., disease, environment, etc.) and does not meet the criteria for a relation with the study product.

8. DATA HANDLING AND RECORD KEEPING

8.1 Data Collection

Data collection will be achieved through a combination of subject and physician reporting with the aid of automated reminders and MSL contact. All data and study-specific forms (including eICF and eCRF forms), will be centralized electronically via *REDCap* (Research Electronic Data Capture Software) *Cloud*. A pdf copy of the ICF will be emailed to subjects for their own records. Access to *REDCap Cloud* will be password-protected and all subjects and physicians will be required to register with a unique username and password.

Physicians will be trained on use of *REDCap Cloud* during Investigator training and ensure that subjects understand and are able to use *REDCap Cloud* software. *REDCap Cloud* is accessible by computer, tablet, or smartphone. Subjects who elect to complete at-home follow-up assessments online will receive an automated email 1 week prior and the day of at-home follow-up with a reminder to complete the questionnaire.

8.2 Data Management

The *REDCap Cloud* system uses a variety of mechanisms for checking data at the time of entry including skip logic, range checks, and data type checks. Upon receipt of new data, the personnel at the Methods Center will query all missing, implausible, or inconsistent data. Study site personnel will be able to conduct a review of open queries in the system and will be trained/required to respond promptly.

8.3 Data Monitoring

Data will be monitored by the Sponsor consistent with International Council for Harmonization (ICH) Good Clinical Practice (GCP) guidelines. Source data verification will be performed remotely on 10% of study sites. Continuous, real-time monitoring of data quality and completeness will be performed remotely by the Sponsor. The registry project management team will periodically review site compliance (completion of scheduled visits and questionnaires), send reminders for missed at-home subject follow-up questionnaires, and guarantee that all efforts are made to contact subjects who discontinue the study or ST treatment prior to 1-year follow-up. Issues with data quality or completeness will be addressed on a case-by-case basis and, if necessary, brought to the attention of the Sponsor when requiring remedial action (e.g., retraining of a site).

8.4 Record Retention

Research data in electronic form will be stored and managed in a secure manner in accordance with applicable federal regulations and guidelines and according to institutional policies and practices. Further, any hard copy documents containing subject data will be stored in secure document containers (file cabinets, lockers, drawers, etc.) in accordance with standard document management practices. At all times, only listed key personnel specifically designated and authorized by the Sponsor shall have access to any research related documents, including electronic data. All such personnel will be properly trained and supervised regarding the management and handling of confidential materials. The Sponsor assumes full responsibility for such training. Site physicians will only have authorization to access data from their respective sites.

8.5 Database Access

The database resulting from this registry is the sole property of Canopy Growth and will only be used for research purposes. During the study, the *REDCap Cloud* database will be accessible to the Sponsor by username and password for the sole purpose of generating summary reports. All forms of data

dissemination will require prior approval from the Sponsor as specified in the Scientific Committee agreement. Site physicians will only have access to their subject's data during the study, but are not permitted to analyze their data or disseminate the results publicly. Site physicians will not have access to the full database; however, a formal request for specific analyses of the entire database can be submitted to the Scientific Committee. Not all requests will be approved.

9. STATISTICAL METHODS

9.1 Statistical overview

The Sponsor will perform statistical analyses. The Sponsor or designee will extract and analyze descriptive data every 6 months. This will be done to keep sites apprised of study progress. A de-identified summary report will be generated and delivered to all registered site physicians.

The report will indicate:

- The number of physician-collaborators stratified by country.
- The number of subjects enrolled stratified by country.
- Subject demographics, chronic pain classification, and treatment goal.
- Subject concomitant medication use.
- Subject ST treatment regimens.
- Incidence of AEs per individual ST product.

Upon database lock a series of analysis will be conducted to address study objectives. For each analysis, the normality of the data distributions will be ascertained using the Shapiro-Wilk test of normality and Levene's test of equality of error variance. Descriptive statistics (frequencies, means, and standard deviations for normally distributed parametric data; medians and interquartile ranges for nonparametric data) will be used to characterize the sample. Outcome analyses will include a change in ST regimen; a change in reported opioid consumption in MME/day; change in daily dose of other medications, including analgesics, sedatives, and benzodiazepines; change in responses to BPI-SF items and EQ-5DL items; initial PGI-C and changes over time; and initial CGI-I and changes over time. For the safety endpoint, AEs will be tabulated descriptively. Detailed analyses are outlined in the Statistical Analysis Plan.

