7. OUTCOME ASSESSMENTS

7.1 Study Endpoints

Primary endpoints

- Physician selection of Spectrum Therapeutics (ST) medical cannabis treatment regimen and changes over time in:
 - (1) average daily dose of THC and CBD (in mg);
 - (2) route of administration (inhaled or ingested).

Secondary endpoints

- Subject selection of ST treatment regimen and changes over time in:
 - (1) average daily dose of THC and CBD (in mg);
 - (2) route of administration (inhaled or ingested).
- Change in BPI-SF responses from baseline.
- Change in EQ5D-5L responses from baseline.
- PGI-C for the target treatment goal.
- CGI-I for the target treatment goal.
- In subjects taking an opioid, changes in opioid use over time (calculated as milligram morphine equivalents [MME]/day).
- Among subjects taking other medication, total daily dose change over time.

Safety endpoint

- Incidence of AEs stratified by product and formulation.

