- Irritability
- Stress

Please indicate the type of sleep disruption that best describes that which is the primary focus of the patient's primary treatment goal

- Increase daytime alertness
- Increase sleep quality or quantity

Please indicate the type of function that best describes that which is the primary focus of the patient's primary treatment goal

- Activities unrelated to employment (e.g. leisure activities)
- Employment related activities (e.g. return to work full time)
- Improve relationships

Concomitant medication

Is your patient currently taking an of the following classes of prescription medication (select all that apply)

- Nonsteroidal Anti-inflammatory Drugs (NSAIDs) and Acetaminophen
- Antidepressants (TCA, SNRI, SSRI)
- Anticonvulsants (gabapentin, pregabalin)
- Muscle Relaxants
- Benzodiazepines
- Opioids
- Other
- Medical Cannabis from a Licensed Producer other than Spectrum

NSAIDs and Acetaminophen Dosing Information

Name of drug

Daily dose of [baseline_visit][nsaid1_name] (total mg per day)

- Check to add additional NSAID /Acetaminophen medications

Name of drug

Daily dose of [baseline_visit][nsaid2_name] (total mg per day)

- Check to add additional NSAID /Acetaminophen medications

Name of drug

Daily dose of [baseline_visit][nsaid3_name] (total mg per day)

Antidepressants Dosing Information

Name of drug

Daily dose of [baseline_visit][antidep1_name](total mg per day)

Check to add additional Antidepressant medications

Name of drug

Daily dose of [baseline_visit][antidep2_name] (total mg per day)

Check to add additional Antidepressant medications

Name of drug

Daily dose of [baseline_visit][antidep3_name] (total mg per day)

Anticonvulsants Dosing Information

Name of drug

Daily dose of [baseline_visit][anticon1_name] (total mg per day)

Check to add additional anticonvulsant medications

Name of drug

Daily dose of [baseline_visit][anticon2_name] (total mg per day)

Check to add additional anticonvulsant medications

Name of drug

Daily dose of [baseline_visit][anticonvu3_name] (total mg per day)

Muscle Relaxants Dosing Information

Name of drug _____

Daily dose of [baseline_visit][musrel1_name] (total mg per day) _____

Check to add additional muscle relaxant medications

Name of drug _____

Daily dose of [baseline_visit][musrel2_name] (total mg per day) _____

Check to add additional muscle relaxant medications

Name of drug _____

Daily dose of [baseline_visit][musrel3_name] (total mg per day) _____

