Benzodiazepines Dosing Information

Name of drug _____

Daily dose of [baseline_visit][benzo1_name](total mg per day) _____

Check to add additional benzodiazepine medications

Name of drug _____

Daily dose of [baseline_visit][benzo2_name] (total mg per day) _____

Check to add additional benzodiazepine medications

Name of drug _____

Daily dose of [baseline_visit][benzo3_name] (total mg per day) _____

Opioid Dosing Information

Please enter MME (total daily morphine equivalent dose in mg) _____

Other Medication Information

Please indicate name of other drugs not included in the above classes _____

Daily dose (total mg per day), if available _____

ST Regimen Canada

[figure not shown]

Please enter in the table below total daily amount of Spectrum Therapeutics products consumed. Please be conscious of the units provided:

Inhaled cannabis = total number of inhalations per day

Ingested oils = total mL per day

Spray format = total number of sprays per day

Capsules & edibles = total number of capsules or total number of chocolate bar squares per day

	Inhaled Formats (dried flower, extract vaporizers) -- report daily total number of inhalations	Ingested Oil Formats - report daily total number of mLs	Spray Formats - report daily total number of sprays	Low Potency Capsule & Edible Formats - report daily total number of low-potency capsules (i.e. 2.5 mg), number of chocolate bar squares, etc.	High Potency Capsule Formats - report daily total number of high-potency capsules
Red (examples include Spectrum #1-4; Tweed Bakerstreet, Highlands, Houdstooth, Donegal; LBS Sunset)	 inhalations  	 mL  	 sprays  	 capsules  	 capsules  
Orange	 inhalations  		 sprays  		
Purple (examples include LBS Ocean View)	 inhalations  		 sprays  		
Blue (examples include Tweed Penelope)	 inhalations  	 mL  	 sprays  	 capsules  	 capsules  
Green (examples include Tweed Argyle)	 inhalations  	 mL  	 sprays  	 capsules  	 capsules  

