- No longer needs/ replaced by medical cannabis
- Unknown

What is their current MME?

Existing Other Medications Dosing Information

At last visit, you indicated that your patient was taking other medications, including [baseline_visit][othmed_name]. Is your patient still taking any of these other prescription medications?

- Yes
- No

Please describe any **changes** to their other existing prescription medications since last visit (including changes to total daily dose)

Concomitant Medications - New

Since last visit, has your patient **started** taking any of the following classes of prescription medication (select all that apply)

- Nonsteroidal Anti-inflammatory Drugs (NSAIDs) and Acetaminophen
- Antidepressants (TCA, SNRI, SSRI)
- Anticonvulsants (gabapentin, pregabalin)
- Muscle Relaxants
- Benzodiazepines
- Opioids
- Other
- Medical Cannabis from a Licensed Producer other than Spectrum

Name of new NSAID/Acetaminophen medication (started since last visit)

Daily dose of [physician_1st_follow][nsaid4_name] (total mg per day)

Name of new antidepressant medication (started since last visit)

Daily dose of [physician_1st_follow][antidep4_name] (total mg per day)

Name of new anticonvulsant medication (started since last visit)

Daily dose of [physician_1st_follow][anticon4_name] (total mg per day)

Name of new muscle relaxant medication (started since last visit)

Daily dose of [physician_1st_follow][musrel4_name] (total mg per day)

Name of new benzodiazepine medication (started since last visit)

Daily dose of [physician_1st_follow][benzo4_name] (total mg per day)

Please enter MME (total daily morphine equivalent dose in mg)

Name of new prescription medication (started since last visit, not covered in above classes)

Daily dose of [physician_1st_follow][othmed4_name] (total mg per day)

Physician AE form

Product information

Do you have any adverse events to report related to this patient?

- Yes
- No

Suspect product(s) name

Start date

_____ (YYYY-MM-DD)

End date

_____ (YYYY-MM-DD)

Route of administration

- oral - oil
- oral - softgel
- oral - spray
- oral - beverage
- oral - chocolate
- oral
- inhalation - smoked
- inhalation - vaporized
- inhalation

Dose (please include amount and unit i.e. mg, ml, #softgels, #inhalations, etc.)

Did reaction disappear after reducing the dose or stopping the product ?

- No
- Yes
- Unknown

Did reaction reappear after same product/treatment was restarted?

- No
- Yes
- Unknown

AE description

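### Section 9.1 promises a separate analysis of sedative dose change, but no form has a sedative class, and drugs entered under 'Other' at baseline get no numeric dose at follow-up

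*Protocol*

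**What the plan says.** The secondary endpoint in Section 7.1 of the Protocol is: "Among subjects taking other medication, total daily dose change over time". Section 9.1 spells out the matching analysis as "change in daily dose of other medications, including analgesics, sedatives, and benzodiazepines", and the synopsis repeats it. Sedatives and benzodiazepines are two separate entries in that list.

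On collection, Section 7.2.6 names these non-opioid classes: "Nonsteroidal Anti-inflammatory Drugs (NSAIDs) and Acetaminophen, Antidepressants, Anticonvulsants, Benzodiazepines and Muscle Relaxants". It adds: "Physicians will be asked to report the medication type and total daily dose, and any changes throughout the study".

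The baseline form (Appendix 1) opens its medication block with "Is your patient currently taking an of the following classes of prescription medication (select all that apply". It offers the same five classes, then opioids, 'Other', and cannabis from another producer. The baseline 'Other' block has two items: "Please indicate name of other drugs not included in the above classes" and "Daily dose (total mg per day), if available".

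The physician follow-up form (Appendix 2) treats 'Other' drugs in two ways. For those already in use it asks whether the patient still takes any of them, then asks for a description of changes "to their other existing prescription medications since last visit (including changes to total daily dose". For one started since the last visit it has a name field and a mg/day field.

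**The concern.** The plan names an analysis category that the forms do not collect. The word sedatives would be redundant if it meant only benzodiazepines, so it presumably covers something more, and whatever falls outside the five classes lands in 'Other'. That block is the one least able to show a change in dose.

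At stake is one part of a stated secondary endpoint and of the secondary objective on changes in other medications (Section 2.1.2). A reduction from baseline can be seen only in a drug already in use at baseline, and for 'Other' that is the case with no numeric follow-up field. An analysis plan can define how doses are compared, but it cannot supply a variable that the form never recorded. The conflict therefore lies within the Protocol and its appendices, whatever an SAP may say.

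**Working it through.** No arithmetic applies and the Protocol gives no figure to reproduce. The check sets the analysis commitment against the form fields. Benzodiazepines serve as the comparator because Section 9.1 names them beside sedatives.

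| Field | Benzodiazepines | 'Other', including a sedative outside the five classes |
|---|---|---|
| Baseline name | 3 per-drug slots | 1 shared item |
| Baseline mg/day | 3 per-drug slots | 1 shared, optional |
| Follow-up, existing: still taking | asked per drug | 1 collective question |
| Follow-up, existing: reason for stopping | asked per drug | not asked |
| Follow-up, existing: current mg/day | asked per drug | no numeric field; 1 free-text item |
| Follow-up, newly started: name | 1 | 1 |
| Follow-up, newly started: mg/day | 1 | 1 |

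The endpoint needs, for each drug, the change D(t) − D(0), where D(0) is the baseline mg/day and D(t) the mg/day at follow-up t. Four cases follow from the table.

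1. *One 'Other' drug, a sedative, dose changed but not stopped.* D(0) is numeric if the optional field was filled in. D(t) exists only if the physician wrote it in the text and someone codes it.
2. *One 'Other' drug, a sedative, stopped.* A 'no' to the collective question gives D(t) = 0. The change is derivable if D(0) was entered.
3. *Two or more 'Other' drugs, one of them a sedative.* The single baseline number cannot be assigned to either drug. If the sedative is stopped and another drug continues, the collective answer is still 'yes'. Neither D(0) nor D(t) for the sedative comes from structured fields.
4. *Sedative started after baseline.* The new-drug fields give name and mg/day at the visit where it is first reported, so this case is captured.

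So structured data give the start of a drug, and the stopping of all 'Other' drugs together. They do not give a dose reduction, a dose increase, or the stopping of one 'Other' drug among several.

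The instruction in Section 7.2.6 to report total daily dose and changes throughout is thus met by numeric fields for the five structured classes, but not for 'Other' drugs already in use.

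**The case against.** The strongest reply is that this is loose wording. The list in Section 9.1 is illustrative, analgesics is not a form class either, and sedatives is nowhere defined. Some drugs meant by the word may already sit among the benzodiazepines, muscle relaxants or antidepressants. Section 7.2.6 also speaks only of medication taken for pain, so sedatives used for other reasons may never have been in view. This stands as a limit on size: the gap concerns only sedatives outside the listed classes, and the documents do not say how many subjects take one. It does not remove the mismatch, because an undefined category that matches no collected class still cannot be reported as written.

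A second reply is that the data exist in another form. Names are recorded and can be coded, the free text expressly asks for dose changes, and Section 8.2 provides for querying missing or inconsistent entries. This also stands in part. A reader might infer that the analysis cannot be done at all; the documents do not support that, since manual recovery is possible. It would be incomplete, though. Range and type checks have no number to act on in a text item, no empty dose field prompts a query, and querying cannot split a shared baseline dose unless the site is asked afresh.

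A reader might also infer that every sedative dose after baseline exists only as text. That is wrong: a newly started 'Other' drug has its own name and mg/day field.

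Finally, a reader might take total daily dose to mean that mg are added across unlike drugs, with distorted totals as the result. The Protocol never says so. The five structured classes record mg/day drug by drug, and Section 9.1 leaves detailed analyses to the SAP. That reading forms no part of this point.

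**Conclusion.** The point holds in a bounded form. Section 9.1 and the synopsis commit to a sedative category that neither Section 7.2.6 nor any form contains. For sedatives outside the listed classes that were in use at baseline, dose change cannot be derived from structured per-drug data, except where every 'Other' drug is stopped and the baseline dose belongs to one drug. Recovery from text is possible but would be incomplete, most clearly with two or more 'Other' drugs.

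The size is modest: one category of one secondary endpoint in a descriptive registry, with the primary endpoints untouched. The number of affected subjects cannot be stated, because the Protocol gives no frequency of sedative use. The matter is still more than wording, since doses not captured during enrolment and follow-up cannot be reliably rebuilt later.

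The conclusion assumes that sedatives is meant to reach beyond the listed classes, as its separate mention beside benzodiazepines suggests. It also assumes that the forms work as printed. Branching logic and later follow-up forms are not fully shown; the piped field names refer to baseline and the first follow-up.

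**What to change.** First, define sedatives in the Protocol, stating which drugs count and how they relate to the existing classes. Then choose one of the following.

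- Add a sedative class to Section 7.2.6 and to Appendices 1 and 2, with the same per-drug name, still-taking and current mg/day fields as the existing classes, at baseline and each physician follow-up. An existing block can be copied.
- Or turn 'Other' into per-drug entries, each with a name and a current dose at every physician visit, and code sedatives from the names.
- If the forms cannot change, rewrite the list in Section 9.1 and the synopsis so that its categories are the classes collected.

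The first two cost a small eCRF change and slightly more data entry at the baseline visit and the four physician follow-ups. The third costs only a text edit, but gives up the separate sedative result. For subjects already enrolled when a form changes, earlier 'Other' entries would still need manual coding, and the report should say so.
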